## **Exclusion criteria**

We will exclude participants on basis on conditions that are contraindicated of training or ability to perform the training program. The exclusion criteria are:

- Physical disability which affects ability to perform the exercises of the training program
- Heart failure or severe degenerative condition, e.g. malignant cancer, multiple sclerosis etc.
- myocardial infarction or stroke the last year
- Heart condition that can worsen with aerobic training, e.g. angina pectoris

Any uncertainties regarding participation that may arise during the baseline test anamnesis will be discussed with the physician in charge of the study.

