# February 16, 2018

## DESCRIPTION OF THE PROPOSED 10-week RANDOMIZED INTERVENTION STUDY

[figure not shown]

Figure 1. Timeline of the two-step intervention which starts with a traditional randomized controlled trial followed by digitalized form of the intervention that is offered the control group.

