## Statistical analysis

Primary analyses will be conducted on an intention-to-treat basis, all participants will be included regardless of whether they completed the follow-up assessment visit. To handle missing data, we will use methodology based on last observation carried forward for participants who did not attend the post-assessment visit. The mean change between pre-intervention and post-intervention measures will be analyzed using the *t*-test when change data are normally distributed otherwise the nonparametric Wilcoxon matched-pairs signed-rank test will be used. Mixed-model analysis will be used to evaluate the change of weight during the intervention to control for relevant covariates. Analyses will be carried out using the SPSS statistical package.

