# February 16, 2018

Inclusion from HAI over 6 month (approximately 400 individuals in total) with about 50 % of the cohort meeting the inclusion criterion generates close to 200 subjects. With a modest assumption of participation rate of 50%, this leave 100 individuals to be randomized into a control group or an intervention group (n=50 per group). For the selected cohort with central obesity in HAI, the mean and SD for VAT-mass is  $2905 \pm 817$  g for men and  $1620 \pm 538$  g for women. Preliminary power calculations based on a 20% decrease in VAT mass,  $\alpha=0,05$  and  $\beta=0.8$  concludes that each group needs to consist of at least 33 subjects for men and at least 45 women. As we will analyze the %-change in VAT over time, we do not need to separate the analysis on sex and thus, there should be enough power to detect the above mentioned changes in VAT mass.

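### No between-arm test is stated for VAT, and the non-normal fallback is a paired test that cannot compare the randomised arms

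*Combined protocol and SAP*

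**What the plan says.** The primary outcome is VAT measured by DXA (Expected outcomes). The Statistical analysis section gives the test in one sentence: "The mean change between pre-intervention and post-intervention measures will be analyzed using the" t-test if change is normally distributed; "otherwise the nonparametric Wilcoxon matched-pairs signed-rank test will be used". It does not say whether the t-test is paired or two-sample, and it does not mention arm, control or a group difference.

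The only model is for another outcome: "Mixed-model analysis will be used to evaluate the change of weight during the intervention to control for relevant covariates". Weight is a secondary outcome, and no arm or arm-by-time term is given.

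The sample-size paragraph that closes the section says "As we will analyze the %-change in VAT over time" the sexes need not be separated, again without naming an arm contrast. The same paragraph randomises 100 people, 50 per group, and concludes that "each group needs to consist of at least 33 subjects for men and at least 45 women". The caption to Figure 1 says the study "starts with a traditional randomized controlled trial".

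**The concern.** Randomisation supports one comparison: change under training against change under control. The signed-rank test on pre/post pairs tests something else, namely whether change within one arm is centred on zero.

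- If the t-test is also meant as paired, the plan contains no randomised comparison of VAT.
- If the t-test is meant as two-sample, a normality check switches the hypothesis from a difference between arms to a change within an arm.

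The distinction matters if VAT can change in both arms without training. Two features in the description of the Healthy Ageing Initiative (HAI) make that plausible. HAI participants receive tailored lifestyle counselling at the one-week follow-up visit, and invitees are selected for high VAT, which invites regression to the mean. How much of either falls inside the 10 weeks is unknown. The Exclusion criteria mention a baseline test ("Any uncertainties regarding participation that may arise during the baseline test anamnesis"), but the documents do not say whether the HAI scan also serves as the trial baseline, or how long after counselling the trial starts. With any common change, a significant fall within the training arm is not evidence that training works.

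**Working it through.** **1. Which test was the trial sized for?**

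Inputs from the sample-size paragraph: VAT mass 2905 ± 817 g (men) and 1620 ± 538 g (women), a 20% decrease, alpha 0.05, and a printed beta of 0.8, read here as power 0.8. Sidedness is not stated; two-sided is tried first.

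Standardised effect:
- Men: d = 0.2 × 2905 / 817 = 581 / 817 = 0.711
- Women: d = 0.2 × 1620 / 538 = 324 / 538 = 0.602

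The normal approximation for two samples, n = 2(1.960 + 0.842)² / d², gives 32 and 44 after rounding up. The t-based results (noncentral t) are:

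| Test | Men per group | Women per group |
|---|---|---|
| Stated in the plan | 33 | 45 |
| Two-sample t, two-sided | 32.03 → 33 | 44.26 → 45 |
| Two-sample t, one-sided | 25.16 → 26 | 34.79 → 35 |
| Paired t, two-sided, SD of change = stated SD | 17.54 → 18 | 23.63 → 24 |
| Paired t, two-sided, SD of change = stated SD × √2 (zero correlation) | 33.01 → 34 | 45.24 → 46 |

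Of these, only the two-sided two-sample t-test gives both stated figures.

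**2. What does a within-arm test do when training has no effect?**

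This is an illustration. The common fall and the pre-post correlation ρ are assumptions; the documents give neither. Equal pre and post SDs and an equal sex mix are also assumed.

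- CVs: men 817 / 2905 = 28.1%; women 538 / 1620 = 33.2%; pooled √[(0.281² + 0.332²) / 2] = 30.8%.
- SD of percentage change = CV × √[2(1 − ρ)], which is 30.8%, 19.5%, 13.8% and 9.7% at ρ = 0.5, 0.8, 0.9 and 0.95.
- Noncentrality of the paired t-test = fall × √50 / SD. For a 3% fall at ρ = 0.9 it is 3 × 7.07 / 13.8 = 1.54.

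Probability that the paired t-test in the training arm (n = 50) gives p < 0.05:

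| Common fall | ρ = 0.5 | ρ = 0.8 | ρ = 0.9 | ρ = 0.95 |
|---|---|---|---|---|
| 0% | 0.050 | 0.050 | 0.050 | 0.050 |
| 1% | 0.056 | 0.065 | 0.080 | 0.110 |
| 2% | 0.074 | 0.110 | 0.172 | 0.297 |
| 3% | 0.104 | 0.188 | 0.327 | 0.570 |
| 5% | 0.203 | 0.429 | 0.712 | 0.945 |

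With one sex's CV, the range for a 3% fall becomes 10% to 51% (women) or 12% to 65% (men).

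The signed-rank fallback behaves alike. In 4,000 simulated trials per setting at ρ = 0.5, 0.9 and 0.95, it rejects in 0.057 / 0.076 / 0.101 (1% fall), 0.100 / 0.306 / 0.544 (3%) and 0.195 / 0.687 / 0.941 (5%). In the same nine settings, the between-arm rank-sum test rejects in 0.042 to 0.053 and the two-sample t-test in 0.045 to 0.052.

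Concluding benefit when the training arm is significant and control is not does not repair this. With a common shift of 0.28 SD of change (2.7% at ρ = 0.95, since 0.28 × 9.7 = 2.7), that pattern occurs in about 25% of null trials. Over shifts of 0 to 0.5 SD it ranges from about 5% to 25%.

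**3. Does a between-arm test need more people?**

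Taking the CV as the SD of percentage change (ρ = 0.5), a 20% between-arm difference and 50 per arm with complete follow-up, two-sample power is 0.94 (men's CV), 0.85 (women's CV) and 0.90 (pooled).

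**The case against.** **The t-test may be two-sample.** An unqualified t-test on change scores, under intention-to-treat in a trial randomised 50 to 50, is naturally read that way, and the normal branch is then sound. This stands as a possible reading. It does not rescue the fallback, which is named precisely and is paired, nor does it supply a stated arm contrast.

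**The sizing is an inference.** The document never says two-sample, and a paired test with zero pre-post correlation comes very close (33.01 and 45.24). That variant rounds up to 34 and 46, so it does not give the stated figures, and zero correlation between two scans of the same person is implausible. The two-sample reading remains an inference, though a strong one.

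**The error rates presuppose a decision rule the plan does not state.** Nowhere does it say success will be judged within the training arm, and both the common fall and the correlation are assumed. This is fair: the table shows what could happen if the written test were used as evidence of benefit. The mismatch of test and design does not rest on it.

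**Power at 50 per arm is conditional.** It assumes complete follow-up. Last observation carried forward sets non-attenders' change to zero; with 10% or 20% non-attendance in both arms (assumed, as no rate is given), power with the women's CV falls to about 0.81 or 0.75. This stands as a caveat on power. It does not mean that stating a between-arm test calls for a larger sample.

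**A rank-sum fallback does not generally test a mean difference.** Correct. It matches the t-test's question only under a location shift, but unlike the signed-rank test it does compare the arms.

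**Conclusion.** The concern holds. No between-arm test of VAT is stated, and the named fallback cannot compare two independent arms under either reading of the t-test. This is an error as written, not just brevity, and it affects the primary outcome. It also leaves the analyst free to choose between within-arm and between-arm testing after seeing the data.

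The conflict with the sizing is firm once the printed beta is read as power and the test as two-sided. The error-rate inflation is conditional: it is nil with no common change, and reaches 10% to 57% for a common 3% fall under the assumptions above. The plan should be corrected before VAT is analysed.

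**What to change.** - State that the primary analysis is the difference between arms (training minus control) in percentage change in VAT, with a 95% CI and two-sided p-value. Name the t-test as two-sample.
- Replace the signed-rank fallback with a between-arm test, such as the Wilcoxon rank-sum test on change. Alternatively, pre-specify one baseline-adjusted model with terms for arm, baseline VAT and sex, which removes the normality-driven switch.
- Report within-arm changes as descriptive only.
- If the mixed model for weight is kept, state its arm-by-time term.
- State which scan is the trial baseline and when it is taken relative to the HAI counselling visit.

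The cost is SAP wording. No new data are needed, and the change adds no sample-size requirement because the stated group sizes already correspond to a two-sample test.

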# February 16, 2018

Inclusion from HAI over 6 month (approximately 400 individuals in total) with about 50 % of the cohort meeting the inclusion criterion generates close to 200 subjects. With a modest assumption of participation rate of 50%, this leave 100 individuals to be randomized into a control group or an intervention group (n=50 per group). For the selected cohort with central obesity in HAI, the mean and SD for VAT-mass is  $2905 \pm 817$  g for men and  $1620 \pm 538$  g for women. Preliminary power calculations based on a 20% decrease in VAT mass,  $\alpha=0,05$  and  $\beta=0.8$  concludes that each group needs to consist of at least 33 subjects for men and at least 45 women. As we will analyze the %-change in VAT over time, we do not need to separate the analysis on sex and thus, there should be enough power to detect the above mentioned changes in VAT mass.

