## **IDENTIFYING INDIVIDUALS ELIGIBLE FOR THE PRESENT INTERVENTION STUDY - short description of HAI**

All individuals residing in the Umeå municipality is invited to HAI when they turn 70 years old. So far, over 3500 individuals have participated in the study with a participation rate over 70%. The participants visit the clinic at 2 occasions a week apart (please see Johansson et al.(17), for further details surrounding the test procedure). At the first visit, traditional and potential novel risk factors for non-communicable diseases are collected, blood samples sent for analyses, and they go home with accelerometers to collect data on physical activity and sedentary behavior. At the one-week follow up visit the participants receive, based on the test results, a tailored intervention aiming at decreasing the risk of diabetes and cardiovascular diseases through counseling regarding main risk factors such as physical inactivity, unhealthy diet, tobacco use and harmful use of alcohol. The basis in the therapy is a cognitive behavioral therapeutics approach using motivational interviewing(18) and prescription-based exercise(19).

We will invite those that have central obesity defined as more than 1 kg for women or 2 kg for men of VAT-mass (approximately 50% of the total cohort) at the visit to HAI. The cut-offs used for VAT mass translates the cut-off values that have been proposed for waist circumference (88 cm for women and 94 for men). Based on visitors from the last 6 month (400 men and women), around 200 will meet the inclusion criteria.

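### The primary test on VAT is not clearly a comparison of the randomized arms: its non-normal fallback works within one group, whereas the sample sizes imply a two-sample test

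*Combined protocol and SAP*

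**What the plan says.** The primary outcome is visceral adipose tissue (VAT) by DXA. On the test, the Statistical analysis section says: "The mean change between pre-intervention and post-intervention measures will be analyzed using the" t-test if the changes are normally distributed, and "otherwise the nonparametric Wilcoxon matched-pairs signed-rank test will be used". It does not say whether the t-test is paired or compares the two arms. A mixed model with covariates is named for weight only.

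The sample-size paragraph that closes the section expects "100 individuals to be randomized into a control group or an intervention group (n=50 per group"). It takes VAT mass in the centrally obese HAI cohort as 2905 ± 817 g in men and 1620 ± 538 g in women. With a 20% decrease, alpha 0.05 and a beta printed as 0.8, it "concludes that each group needs to consist of at least 33 subjects for men and at least 45 women". It then turns to percentage change with the sexes pooled: "we do not need to separate the analysis on sex and thus, there should be enough power to detect the above mentioned changes". It gives no SD of percentage change, no pre-post correlation and no power figure for that analysis.

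**The concern.** The design is a randomized comparison of training with control, so the primary test should compare the arms. A matched-pairs signed-rank test asks whether change within one set of people is centred on zero. Run in each arm, it gives two separate answers and no test of the difference between them.

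This matters here because VAT may fall in both arms for reasons other than training. Entry requires high VAT ("central obesity defined as more than 1 kg for women or 2 kg for men of VAT-mass"), so some regression to the mean is possible if the screening scan serves as baseline. The HAI programme also gives its participants tailored lifestyle counselling at the one-week visit. A significant fall within the training arm could therefore occur without any effect of the training programme.

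A second gap follows. The printed sizes concern one sex and use the spread of VAT grams between people. The planned analysis pools the sexes and uses percentage change, whose spread is not given. A reader cannot see from the plan what between-arm difference 50 per arm can detect.

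**Working it through.** **1. Reproduce the plan's sizes.** Inputs from the sample-size paragraph: means 2905 and 1620 g, SDs 817 and 538 g, a 20% difference, alpha 0.05. Assumed: two-sided test, power 0.80.

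- Differences: 0.20 × 2905 = 581 g; 0.20 × 1620 = 324 g.
- Standardized: 581/817 = 0.711; 324/538 = 0.602.
- Normal approximation, n = 2 × [SD × (1.960 + 0.842)/difference]²: 31.04 for men and 43.28 for women, so 32 and 44.
- Two-sample noncentral t: 32.03 and 44.26, so **33 and 45**, an exact match (power 81.2% and 80.7%).

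The alternatives do not match:

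| Variant | Men | Women |
|---|---|---|
| Paired or one-sample t, same SDs | 18 | 24 |
| One-sided 0.05, two-sample t | 26 | 35 |
| Beta of 0.8 taken literally (power 0.20), normal approximation | 5 | 7 |

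The sizes therefore imply a two-sided, two-sample test at power 0.80, and the printed beta is a labelling slip.

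**2. What the SDs represent.** For change, SD(change) = SD × √[2(1 − r)], where r is the pre-post correlation and the SD is the same at both times. At r = 0.5 the factor is 1. The same 33 and 45 would thus arise for VAT grams at one time point or for change in grams at r = 0.5. The text does not say which was meant.

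**3. Carry over to pooled percentage change.** Coefficients of variation: 817/2905 = 0.281 and 538/1620 = 0.332. Assuming equal numbers of each sex, pooled CV = √[(0.281² + 0.332²)/2] = 0.308. To first order:

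- unadjusted SD of percentage change = 0.308 × √[2(1 − r)];
- SD after adjustment for baseline = 0.308 × √(1 − r²).

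Power of a two-sided 0.05 between-arm t-test, 50 per arm, 20-point difference, equal SDs in the arms, no missing visits:

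| Assumed r | SD unadjusted | SD adjusted | Power unadjusted | Power adjusted |
|---|---|---|---|---|
| 0.3 | 0.364 | 0.294 | 78% | 92% |
| 0.5 | 0.308 | 0.266 | 90% | 96% |
| 0.7 | 0.238 | 0.220 | 98.6% | 99.5% |

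No extra gain is credited to sex.

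**4. SD that the design can bear.** At 50 per arm and a 20-point difference, 80% power between arms needs an SD of percentage change of at most 35.3 points. By the formula in step 3 this corresponds to r of about 0.34. Examples: SD 30 gives 91.0%, SD 35 gives 80.8%, SD 40 gives 69.7%. A paired test within one arm of 50 would tolerate about 49 points, but it answers a different question.

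**The case against.** The strongest reply is that the intended test can be inferred. The sizes fit only a two-sample test, and they are given for each group directly after a control and an intervention group are named. That stands: what was powered is reasonably clear. It does not settle the analysis text, which names a within-group procedure for non-normal data and leaves the t-test open.

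It can also be said that the calculation is called preliminary, that 100 participants follow from recruitment (400 × 50% × 50%), and that rewording changes no numbers enrolled. This is fair. The missing SD and the beta label would be reporting details if they stood alone.

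An unadjusted between-arm t-test is valid under randomization, so adjustment is an improvement rather than a correction, and at a correlation of 0.7 or above it adds almost nothing. It might be added that the HAI screening scan need not be the trial baseline. But percentage change cannot be computed without a baseline VAT value, so the covariate will be available in any case.

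A reader might infer that 33 and 45 are miscalculated, or that the trial is underpowered. The documents support neither. The sizes reproduce exactly, and 50 per arm gives at least 80% power unless the SD of percentage change exceeds about 35 points; nothing in the text shows that it does. Nor do the documents establish that the sponsor meant single-time grams, since change in grams at correlation 0.5 gives the same sizes.

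**Conclusion.** The concern holds as a mismatch between analysis and design. The t-test is not stated to compare arms, the matched-pairs fallback cannot do so, and the sizes belong to a between-arm test. This should be corrected before analysis.

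The possible gain from adjustment is about 14 percentage points of power at correlation 0.3, 6 at 0.5 and 1 at 0.7. These figures rest on assumptions that the documents do not supply: the correlation, an equal sex mix, equal SDs in the arms and at both times, a true difference of 20 points, and no missed post-intervention visits. The plan carries the last observation forward for missed visits, which with one pre and one post measurement sets change to zero and would dilute the difference; no rate is stated.

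**What to change.** In the Statistical analysis section:

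- State that the primary analysis is the between-arm difference in percentage change (or log) VAT, adjusted for baseline VAT and sex.
- Replace the matched-pairs fallback with a between-arm one, for example analysis on the log scale or a rank-based between-group test.

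In the sample-size paragraph:

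- Write power 0.80 (beta 0.20).
- Note that 33 and 45 are within-sex sizes that use the between-person SD of VAT grams, equivalent to change at correlation 0.5.
- Give the power for pooled percentage change at 50 per arm, with the assumed SD or correlation range, its source and the assumed rate of missed visits.

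The cost is a few sentences, with no added participants or measurements. The restated detectable difference may turn out larger or smaller than 20%.

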## Ethical considerations

Only the research leader will have access to social security numbers from where the identity can be traced from individual data. No individual data will be presented. Permission for this study will be obtained from the Umeå University Research Ethics Committee and will conform to the World Medical Association Declaration of Helsinki.

## Clinical relevance

There are great health gains to be made when overweight persons starts training, including; reduced risk of hypertension and high blood lipids, reduced risk of diabetes and cardiovascular disease. If you already suffer from high blood pressure or diabetes then increased physical activity is a common treatment as it has been shown to improve the condition. Furthermore, after the initial control period, the control group is also offered to receive training and thus the health effects that may arise as a consequence thereof.

Last, there is an urgent need to find an effective, inexpensive and evidence based method to treat patients with central obesity. Hopefully, our study can demonstrate the effectiveness of a digitalized training program that hopefully can be distributed to patients in need of reducing their central obesity towards a healthier life.

